5.2 Analysis Sets

The following analysis populations are defined for this study:

Safety Population

All subjects who received at least one dose of any study drug (either MT-3724, or lenalidomide) will be included in the safety population. The safety population will be used for the primary statistical analysis of safety and efficacy endpoints.

Efficacy Evaluable Population

The efficacy evaluable population will include patients who have at least one post-baseline radiographic evaluation or those that were discontinued for clinical progression.

PK Population

The PK population will include all subjects who received at least one dose of MT-3724 and have at least one post-baseline PK assessment. The PK population will be used for the PK analyses.

Subjects who received only lenalidomide but haven't received MT-3724 will be excluded from the PK analyses.

Immunogenicity Population

All subjects who received at least one dose of MT-3724 and have at least one post-baseline immunogenicity assessment will be included in the analyses of anti-drug antibody (ADA) and NA. Subjects who received only lenalidomide but haven't received MT-3724 will be excluded from the immunogenicity analyses.

PD Population

All subjects who received at least one dose of MT-3724 and have at least one post-baseline PD assessment will be included in the analyses of B-cell count and immunophenotype (flow cytometry). Subjects who received only lenalidomide but haven't received MT-3724 will be excluded from the PD analyses.

5.3 Assessment Windows

Data will be summarized based on the CRF (Study Visit) in which it was collected even if the assessment is outside of the specified visit window. In data listings, the relative day of all dates will be presented. Such days will be measured relative to Day 1, the day in which the first dose of study drug is received.

The last post-baseline visit where data were collected will be flagged for each subject. These visits will be combined for analysis of laboratory and vital sign results.

The assessment obtained at the most recent time before the start of MT-3724 treatment will be the baseline for all post-baseline assessments. The value obtained before MT-3724 Dose 1 on C1D1 (if available) will serve as the baseline; if not available, then the value obtained earlier at screening

will serve as the baseline. Screening procedures should be performed up to 28 days before Day 1 C1D1.

If a repeat laboratory sample was drawn for a visit, the values from the repeat sample will be used for summary and analysis purposes. In this case, only the repeat sample values will be listed.

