6.4 Laboratory Tests

The following laboratory tests are to be performed as indicated by the Schedule of Assessment and Safety Laboratory Panel.

The following tests will be performed by the central laboratory:

- Hematology
- Chemistry (with eGFR)
- HbA1c
- Coagulation
- Thyroid function
- Beta-2 microglobulin
- Serum cytokines
- Complement
- Immunoglobulins
- Histamine
- B-cell count and immunophenotype (flow cytometry)
- Immunogenicity of MT-3724; Anti-drug antibodies (ADA and NAb titer)

- Serum RTX concentration (if applicable)

The following laboratory tests will be performed by a local laboratory:

- Urinalysis (dipstick)
- Pregnancy test (serum or urine)
- Serology/Virology for HIV, HBV and HCV (if applicable)

The same laboratory should analyze all scheduled laboratory tests throughout the study.

In the event of an unexplained clinically-significant abnormal laboratory test value, the test should be repeated immediately and followed up until it has returned to the normal range and/or an adequate explanation of the abnormality is found. Any clinically-significant laboratory abnormality considered an AE should be recorded in the eCRF.

A standalone Laboratory Manual will provide complete instructions regarding how these samples should be collected, stored and shipped.

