7.8.1 Safety data handling

Adverse events

All AEs will be coded according to MedDRA and graded for severity using the CTCAE v.5.0.

Treatment-emergent adverse events (TEAEs) and treatment-emergent serious adverse events (TESAEs) are defined as those AEs/SAEs that occurred or worsened at or after the start of the first infusion of the first study drug. The occurrence of TEAEs and TESAEs will be reported up until the STFU Visit.

Only TEAEs and TESAEs will be summarized. The incidence of TEAEs will be presented using the number and percent of subjects who experienced the AE using MedDRA (overall incidence, System Organ Class and preferred term) and the worst CTCAE grade. The incidence of the following TEAEs and drug-related TEAEs will be summarized by treatment group / cohort: Overall, TEAEs leading to dose interruption, dose delay, dose reduction, permanent discontinuation, IRR, CRS, and CLS. The TESAEs will be summarized similarly.

Individual listings of DLTs will be presented by MT-3724 dose cohort in Part 1, with the AE term, MedDRA terms, treatment cycle of onset, serious or non-serious and severity grade (CTCAE v.5.0) provided for each DLT.

The pre-treatment AEs include those AEs that occurred due to study-related procedures. These AEs will be assessed by verbal probes and from medical history. The pre-treatment AEs will be listed by subject but not summarized.

Laboratory safety tests

Laboratory results will be summarized by treatment group/cohort using absolute values and change from baseline; or presented as per-subject listings. The incidence of laboratory data outside the reference range (L, H) will be summarized in frequency tables by treatment group/cohort. Further details will be provided in the SAP.

Physical examination

The overall results of the physical examination ('normal', 'abnormal, NCS', or 'abnormal, CS') will be summarized by treatment group/cohort and listed per subject. Comments for abnormal CS results will be listed.

Other safety variables

Quantitative data for other safety variables will be summarized by the following descriptive statistics: arithmetic mean, standard deviation, median, minimum, and maximum. These summary statistics will be presented by the treatment group/cohort for the absolute values and changes from baseline. Frequency tables will be provided for qualitative data.

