8.2.6 Adverse Event Summaries

All AEs (serious and non serious) occurring after completion of the informed consent process and before the end of study, regardless of relationship to study drug, will be included and classified by system organ class (SOC) and preferred term (PT) using the Medical Dictionary for Regulatory Activities (MedDRA).

For treatment-emergent AEs (TEAEs), the following will be summarized and presented for the safety analysis set:

- i. An overall summary of TEAEs, which includes:
 - a. the number and percentage of subjects experiencing a TEAE
 - b. the number and percentage of subjects experiencing a TEAE by relationship to study medication (for each study medication)
 - c. the number and percentage of subjects experiencing a TEAE by greatest grade
 - d. the number and percentage of subjects experiencing a TEAE leading to study dose interruption
 - e. the number and percentage of subjects experiencing a TEAE leading to dose delay
 - f. the number and percentage of subjects experiencing a TEAE leading to dose reduction
 - g. the number and percentage of subjects experiencing a TEAE leading to study withdrawal
 - h. the number and percentage of subjects experiencing a TEAE of special interest (IRR, CRS, and CLS)
 - i. the number and percentage of subjects experiencing a treatment emergent SAE (TESAE)
- ii. the number and percentage of subjects experiencing a TEAE by SOC, PT
- iii. the number and percentage of subjects experiencing a TEAE by SOC, PT and relationship to study medication (for each study medication)
- iv. the number and percentage of subjects experiencing a TEAE by SOC, PT and greatest grade

- v. the number and percentage of subjects experiencing a TEAE leading to dose interruption by SOC and PT
- vi. the number and percentage of subjects experiencing a TEAE leading to dose delay by SOC and PT
- vii. the number and percentage of subjects experiencing a TEAE leading to dose reduction by SOC and PT
- viii. the number and percentage of subjects experiencing a TEAE leading to study withdrawal by SOC and PT
- ix. the number and percentage of subjects experiencing a TEAE of special interest by SOC and PT
- x. the number and percentage of subjects experiencing a TESAE leading to dose interruption by SOC and PT
- xi. the number and percentage of subjects experiencing a TESAE leading to dose delay by SOC and PT
- xii. the number and percentage of subjects experiencing a TESAE leading to dose reduction by SOC and PT

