8.3 Clinical Laboratory Assessments

Laboratory assessments will be summarized by presenting descriptive statistics of raw data and change from baseline. Listings will include flags for values outside of the reference ranges, and clinical significance if a laboratory result is deemed abnormal.

The following tests will be performed by the central laboratory:

- Hematology
- Chemistry (with eGFR)
- HbA1c
- Coagulation (aPTT and either INR or PT)
- Thyroid function (TSH and FT4)
- Serum cytokines
- Histamine
- Complement
- Immunoglobulins
- B-cell count and immunophenotype (flow cytometry)

The following laboratory tests will be performed in the local laboratory at the site:

- Urinalysis (Dipstix)
- Pregnancy test (serum or urine)
- Serology for HIV, HBV and HCV (if applicable)

A shift table displaying baseline CTCAE grade to maximum post-baseline CTCAE grade will be presented for hematology and chemistry lab values.

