8.5 Vital Signs

Vital sign data including weight, systolic blood pressure, diastolic blood pressure, heart rate, and temperature, will be summarized by presenting descriptive statistics of raw data and change from baseline values at each visit.

A shift table displaying baseline to maximum post-baseline values and last post-baseline value will be presented.

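### SAP 5.3 keeps only the repeat laboratory sample, so laboratory tables and listings can understate worst grade; SAP 8.2.6 also counts withdrawal from the study where the protocol requires permanent discontinuation.

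*SAP*

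**What the plan says.** **Laboratory repeats.** Under SAP 5.3, once a visit has a repeat laboratory sample, the values from that repeat "will be used for summary and analysis purposes. In this case, only the repeat sample values will be listed". SAP 8.3 then plans this output: "A shift table displaying baseline CTCAE grade to maximum post-baseline CTCAE grade will be presented for hematology and chemistry lab values". On when to repeat, Protocol 6.3.5 (clinical laboratory adverse events) asks that clinically significant out-of-range results be verified by a prompt repeat. For an unexplained, clinically significant abnormality, Protocol 6.4 says "the test should be repeated immediately and followed up until it has returned to the normal range", or until it is adequately explained. Protocol 7.2 promises that all data will appear in listings. SAP 4 gives the SAP's statistical methods precedence over the protocol.

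**Discontinuation.** Among the required TEAE summaries, Protocol 7.8.1 lists "TEAEs leading to dose interruption, dose delay, dose reduction, permanent discontinuation, IRR, CRS, and CLS". SAP 8.2.6 instead gives "the number and percentage of subjects experiencing a TEAE leading to study withdrawal" (item i.g), and uses the same category for TEAEs by SOC and PT (viii) and for TESAEs (xiii).

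**Vital signs.** SAP 8.5: "A shift table displaying baseline to maximum post-baseline values and last post-baseline value will be presented". It also gives descriptive statistics and changes from baseline by visit. Its list of vital signs leaves out respiratory rate, which Protocol 7.8.1 includes.

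**The concern.** Safety and tolerability is the primary objective. The primary endpoint names laboratory abnormalities, and Protocol 7.8 counts laboratory and vital-sign results among the bases of the primary safety analysis. A rule that keeps the repeat and discards the first value would do little harm if repeats were random. Here the trigger is a bad result, so the discarding is selective. Because the listing drops the value too, a reader of the study report could not detect the loss.

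The discontinuation tables matter for a different reason. How often toxicity forces a drug to be stopped is a core tolerability result, and in a two-drug regimen it is needed for each drug.

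**Working it through.** The plan states no figure on this point, so there is nothing to reproduce. The check is mainly a reading of the passages side by side.

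**1. Tracing a laboratory value (hypothetical).** Haematology is due on D1, D8 and D15 of each cycle (Protocol 6.4.1). Suppose the D15 neutrophil count is 400/µl, which is Grade 4 by the limit of 500/µl in Protocol Appendix 4, and the repeat for that visit is 1,600/µl.
- By-visit summary: 1,600.
- Listing: 1,600 only.
- Maximum-grade shift table: D15 contributes the grade of 1,600.
- AE tables: Protocol 6.3.5 generally makes a Grade 3 or 4 result an AE once it is confirmed. This one was not, so reporting rests on the investigator's judgement of clinical significance.

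If it is not reported as an AE, the value appears in no output.

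**2. Tracing a treatment stop under SAP 8.2.6.**

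| Subject | Required by Protocol 7.8.1 | Study withdrawal read literally | Read as leaving treatment |
|---|---|---|---|
| Stops both drugs for toxicity and is followed for PFS and OS (Protocol 3.5) | counted | not counted | counted |
| Stops LEN alone for toxicity and continues MT-3724 (Protocol 5.2.2) | counted | not counted | not counted |

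Neither reading delivers the protocol's summary. The SAP's AE listing does not fill the gap: it flags whether an event led to withdrawal but carries no action taken per drug.

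**3. Vital signs.** Blood pressure is taken at 0.5, 1 and 2 hours after the start of each infusion (Protocol 6.2.6). Protocol 1.2.1 names hypotension as part of capillary leak syndrome. A fall that has recovered by the last visit enters neither the maximum nor the last-value column of the shift table.

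**4. How far the two laboratory rules could diverge (illustration; none of these inputs is in the documents).** Assume that first and repeat values are bivariate normal with correlation ρ, that nothing truly changes between draws, that a share p of values crosses a threshold c = Φ⁻¹(1−p), and that every crossing value is repeated. The share still crossing on the repeat is [1 − 2Φ(c) + Φ₂(c, c; ρ)] / p:

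| p | ρ = 0.5 | ρ = 0.7 | ρ = 0.9 |
|---|---|---|---|
| 0.05 | 0.244 | 0.392 | 0.637 |
| 0.10 | 0.324 | 0.468 | 0.689 |
| 0.20 | 0.436 | 0.565 | 0.750 |

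A shift table counts subjects, not values. Simulating 200,000 subjects with within-subject correlation 0.5, 3 or 6 visits and p of 0.05 or 0.10, the share who ever cross is 11.8% to 32.3% if the worst value is kept and 2.9% to 23.8% if the repeat replaces it. The second count is 25% to 74% of the first. For 40 subjects, p = 0.10, 6 visits and ρ = 0.7, this is 40 × 0.323 = 12.9 against 40 × 0.165 = 6.6.

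Because no true change is assumed, part of this gap is ordinary variation between draws. It shows how far the two rules can part, not how much toxicity would be lost.

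**The case against.** The strongest defence is that the endpoint counts do not come from the laboratory dataset. The TEAE, grade, relatedness and SAE tables use investigator-reported events, DLTs have their own table and listing (SAP 8.2.7), and dose decisions rest on ongoing data review. This stands. A reader might infer that the primary safety tables as a whole understate toxicity, but the documents do not support that. SAP 5.3 overwrites no AE record. The defence weakens only for a value not confirmed on repeat, since confirmation is the usual route into the AE tables.

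The protocol's follow-up until normal applies to unexplained abnormalities and also ends with an explanation. A later recheck might be recorded as unscheduled rather than as a repeat for the visit. Both points are fair. The SAP does not define the difference, which is itself a gap.

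On discontinuation, SAP 3.1 describes only screening and treatment periods, so withdrawal there may mean leaving treatment. Protocol 4.3.1 speaks of withdrawal from the treatment period, and SAP 6.1 tabulates reasons for not completing study medication. This softens the point but does not remove it: SAP 6.1 gives neither the causative TEAEs by SOC and PT nor a split by drug. A reader might infer that the withdrawal counts would be close to zero; that depends on a reading the SAP does not settle.

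On vital signs, a reader might infer that only maxima are shown. In fact the last value is also in the shift table, and the by-visit statistics include the minimum across subjects (SAP 5). Clinically significant changes are reported as AEs. What remains is one missing column and one missing variable.

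**Conclusion.** The laboratory rule is wrong as written. It can understate worst grade in the laboratory summaries, listings and grade-shift table, and it conflicts with the protocol's promise to list all data. The direction is likely rather than certain, because a repeat can be worse than the first value. The effect does not extend to overall TEAE or DLT counts.

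The documents do not allow a size. A reader might assume shares of values repeated and recovered and subtract the product from the 30% to 66% neutropenia range in Protocol 1.3.1. That fails three times: the shares are not in the documents, the range comes from rituximab-lenalidomide studies, and a loss of values is not an equal loss of subjects.

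The discontinuation mismatch is separate and real, and most clearly so when one drug is stopped alone. The vital-sign gaps are minor. Nor do all these rules lean one way: the maximum is the adverse direction for weight gain, fever and fast heart rate, and leaving out respiratory rate is a matter of completeness. The laboratory and discontinuation rules should be corrected before the tables are programmed.

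**What to change.** - **SAP 5.3 and 8.3:** list every laboratory sample. Define a repeat as distinct from an unscheduled sample. Use the worst valid post-baseline value, including repeats and unscheduled samples, for grade shifts. Replace a first value only when the laboratory declares that sample invalid.
- **SAP 8.2.6, items i.g, viii and xiii:** tabulate TEAEs and TESAEs leading to permanent discontinuation of MT-3724, of LEN and of both. If withdrawal from the study is also wanted, show it separately. Protocol 6.3.6 already has action taken recorded for each drug.
- **SAP 8.5:** add each subject's minimum blood pressure to the shift table, and add respiratory rate to the vital signs summarised.

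The cost is SAP wording and programming, with no new data collection. The tables may look slightly less favourable.

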5.5 Multiple Comparisons

There are no multiple comparisons.

5.6 Data Derivations and Transformations

Not applicable.

6. STUDY PATIENTS

6.1 Disposition of Subjects

A table of counts of all safety subjects will be provided. Reasons for not completing study medication as planned and reasons for premature withdrawal will be tabulated by dose level.

6.2 Protocol Deviations

Distribution for the types of protocol deviations and the number of subjects that deviate from the protocol will be tabulated for the dose levels.

6.3 Demographic Characteristics

Descriptive statistics will be used to summarize the demographic characteristics (age, gender, race, ethnicity, weight, and height) for the safety analysis set.

6.4 Baseline Characteristics

Subject baseline characteristics; including demographics, medical history, physical examination, ECG, and vital signs will be summarized descriptively.

6.5 Medical History

All medical conditions and surgical procedures will be classified by system organ class (SOC) and preferred term (PT) using the Medical Dictionary for Regulatory Activities (MedDRA). Medical history will be categorized into either non-cancer related or cancer related. Summaries and listings of each category will be presented separately.

6.6 Prior and Concomitant Medications

Prior medications within 30 days of consent and inter-current concomitant medications will be coded using World Health Organization (WHO) drug classifications. The number and percent of safety subjects using concomitant medications will be tabulated by Anatomical, Therapeutic, and Chemical (ATC) class and by preferred name.

All prior and concomitant medication data will be listed, sorted by dose level, investigative site and subject number, start and stop date. Information listed will include medication, indication, dose, and route of administration.

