5.1.4 Premedication before MT-3724 infusion

One premedication agent from each of the following 3 therapeutic classes must be given within 60 minutes before the start of each MT-3724 infusion in cycle 1 in both parts of the study:

- Oral anti-pyretic agent (325 – 1000mg acetaminophen or equivalent)
- Intravenous H1 histamine receptor antagonist (50 – 100mg diphenhydramine or equivalent)
- Intravenous corticosteroid agent with a shorter biological half-life (125 – 1000mg methylprednisolone or equivalent)

The specific drugs in each class should be selected at investigator's discretion or according to the institutional guideline. Cases where a subject has a contraindicating medical condition that precludes pretreatment with any of the categories above should be discussed with the sponsor. Although continued pre-medication is recommended during all cycles, after cycle 1, the investigator may adjust the dosage and/or avoid using certain premedication agents during the treatment, if supported by the investigator's assessment of the risk from infusion-related reaction, anaphylaxis or other hypersensitivity events.

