6.2.2 Prior and concomitant medications

Any medication (both prescription and over-the-counter [OTC] medications and supplements, and palliative treatments such as radiation or intrathecal chemotherapy, when permitted), used within 4 weeks prior to the start of treatment until the STFU Visit will be recorded in the eCRF, together with the main reason for its prescription.

The medications taken before the start of treatment on C1D1 will be regarded as prior medications (prior NHL therapy will be captured separately, [Section 6.1.5](#)). The prior medications will be captured at the following time points:

- During the screening period
- Before the start of treatment on C1D1.

The medications taken after the start of treatment on C1D1 will be regarded as concomitant medications. Concomitant medications will be captured at all visits and telephone contacts from the start of treatment until the STFU Visit.

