7.3 Sample size justification

Approximately 64 subjects (i.e., 24 subjects in Part 1 and approximately 40 subjects in Part 2), as well as the appropriate number of replacements (if needed), will be enrolled and treated in this study. The actual number will depend on the number of dose cohorts needed to identify the MTD of MT-3724 in combination with LEN in Part 1.

No formal power calculation and sample size justification will be performed for this descriptive non-pivotal Phase 2a study. The proposed sample size is deemed sufficient for the adequate characterization of the study objectives and would be typical of the sample sizes of exploratory Phase 1b/2a studies with novel anti-cancer agents.

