7.8 Safety analyses

The primary analysis of safety will be a comprehensive evaluation of AEs and/or toxicity, presented by dose, regimen and tumor type cohort and overall, based on:

- The type, incidence, severity, timing, seriousness, and relatedness of adverse events.
- Incidence of DLT and TEAEs that led to treatment modification
- Recording of IRR, CRS and CLS
- Results of monitoring vital signs (BP, HR, RR and body temperature)
- Results of clinical chemistry, hematology, thyroid function, coagulation, and urine analysis tests
- ECG results
- Changes in physical examination
- Results of immunogenicity assessments ADA and NAb
- Need for concomitant medications

All safety analyses will be descriptively summarized based on the safety population.

AEs/SAEs will be coded and tabulated using the current version of MedDRA. Each AE will be classified by system organ class and preferred term. All AEs along with the coded terms will be listed.

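### SAP 6.6 does not separate MT-3724 premedication from medication given for adverse events, so three class rows cannot show need; separately, its prior-medication window conflicts with the protocol's

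*SAP*

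**What the plan says.** Protocol 7.8 lists "Need for concomitant medications" among the components of the primary safety analysis. The table planned for medications is in SAP 6.6: "The number and percent of safety subjects using concomitant medications will be tabulated by Anatomical, Therapeutic, and Chemical (ATC) class and by preferred name". That section has no split by indication and no rule for premedication. It also plans a listing, of which it says: "Information listed will include medication, indication, dose, and route of administration".

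Protocol 5.1.4 states, for cycle 1 in both parts: "One premedication agent from each of the following 3 therapeutic classes must be given within 60 minutes before the start of each MT-3724 infusion". The classes are an oral antipyretic, an intravenous H1 antagonist and an intravenous corticosteroid. Later premedication is recommended but adjustable.

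Protocol 6.2.2 says of any medication: "used within 4 weeks prior to the start of treatment until the STFU Visit will be recorded in the eCRF, together with the main reason". It divides prior from concomitant at the start of treatment on C1D1 and makes no exception for premedication.

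On prior medication, SAP 6.6 says: "Prior medications within 30 days of consent and inter-current concomitant medications will be coded". It does not say when a medication becomes concomitant. SAP section 4 gives the SAP's methods precedence over the protocol.

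**The concern.** The three premedication classes are also ones that could be used to treat IRR or CRS. A table that counts any use puts a corticosteroid given as required before an infusion in the same row as one given for a reaction. Protocol 5.9 itself distinguishes these two uses of immune modulators, but the SAP table does not. At stake is whether a named component of the primary safety analysis can be read for those classes, by dose cohort.

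The second issue is separate. The SAP's prior-medication period and the period for which the eCRF collects data start and end at different points. With no stated start for concomitant use, the programmer has to decide where a medication taken between consent and first dose belongs.

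**Working it through.** **The plan's own figures.** There is nothing to reproduce on this point. Protocol 7.3 says: "No formal power calculation and sample size justification will be performed for this descriptive non-pivotal Phase 2a study". The planned total checks (24 + 40 = 64) but is only context.

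**Check 1: what the three rows would show.**

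Inputs from the documents: protocol 5.1.3 plans 6 infusions in cycle 1 for Cohorts 1-3 and 4 for later cohorts. The first premedication precedes the first infusion and may count as prior. That leaves 6 − 1 = 5 or 4 − 1 = 3 premedication occasions after treatment has started. So a subject with two or more infusions enters all three rows, barring a contraindication, if premedication is entered as concomitant medication.

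Assumed inputs, not given in the documents: m, the share of subjects counted in a row through premedication; q, the share using that class for an adverse event; and independence of the two.

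Row percentage = m + (1 − m) × q

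| m | q = 10% | q = 40% | Difference shown (true: 30 points) |
|---|---|---|---|
| 0.90 | 0.90 + 0.10 × 0.10 = 91% | 0.90 + 0.10 × 0.40 = 94% | 3 points |
| 0.95 | 0.95 + 0.05 × 0.10 = 95.5% | 0.95 + 0.05 × 0.40 = 97% | 1.5 points |
| 1.00 | 100% | 100% | 0 points |

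A tabulation by reason for use would show 10% and 40%.

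The share m may also differ between cohorts. Protocol Appendix 9 records that version 3.0 made premedication compulsory throughout cycle 1, where it had been discretionary, and that dose-limiting toxicities had already occurred in Cohort 2. With q = 10% in two cohorts but m = 0.90 in one and 1.00 in the other, the rows read 91% and 100%. That is a gap of 100 − 91 = 9 points with no difference in need.

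**Check 2: overlap of the two prior-medication periods.**

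Let consent be s days before C1D1. Reading the SAP window as looking back from consent, it runs from day −(s + 30) to day −s. The protocol's pre-treatment collection runs from day −28 to C1D1.

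Overlap = max(0, 28 − s); SAP window outside the collected period = 30 − overlap

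| s (days) | Overlap (days) | SAP window outside collected period (days) |
|---|---|---|
| 0 | 28 | 2 |
| 7 | 21 | 9 |
| 14 | 14 | 16 |
| 21 | 7 | 23 |
| 28 | 0 | 30 |
| 35 | 0 | 30 |

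Protocol 3.2 allows 35 days of screening and SAP 5.3 allows 28. At either maximum, the SAP's prior period contains no day for which the protocol requires collection. Anchoring to C1D1 gives all 28 days for every subject.

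**The case against.** The strongest reply is that the information is available elsewhere. The SAP 6.6 listing carries indication and is sorted by dose level. The adverse event listing in SAP 8.2.6 includes treatment given. The same section tabulates IRR, CRS and capillary leak syndrome (CLS) directly as events of special interest. Need for medication is one of nine descriptive bullets in protocol 7.8, SAP section 8 plans no formal comparison of dose levels, and protocol 7.8.1 asks for a summary by drug class only where appropriate. All of this stands and limits the consequence. It does not make the three rows readable, and a listing is not a summary of a component the protocol names.

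It may also be said that premedication might never reach the table. The Schedule of Assessments places it under study treatment, apart from the concomitant medication review, and the eCRF is not shown. Protocol 6.2.2 points the other way but does not settle it, so the first part of the point remains conditional.

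Three stronger readings are tempting and not supported.

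- A reader might infer that the whole table fails, or that treatment of CLS disappears from it. Only three classes are affected. G-CSF and transfusions (protocol 5.10), and the saline or albumin that protocol 1.6 mentions for hypotension, edema and hypoalbuminemia, lie outside them.
- A reader might infer about 100% in every cohort. The change at version 3.0, contraindications, and lenalidomide-only subjects in the safety population all argue against that.
- A reader might infer that the consent-based window distorts the concomitant table. SAP 6.6 lists prior medications but does not tabulate them, so the overlap figures change no planned percentage directly. The only route is the undefined start of concomitant use, and protocol 6.2.2 supplies a definition if it is taken to apply.

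**Conclusion.** The point holds in limited form, as a minor but worthwhile correction.

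If premedication is recorded as concomitant medication, the corticosteroid, H1-antihistamine and antipyretic rows will be dominated by protocol-required use: near-universal under version 3.0, possibly lower in cohorts treated under the version before it. Those rows cannot show need for treatment of IRR or CRS and should not be compared across cohorts. On the assumed rates, a 30-point difference shrinks to between 3 and 0 points. The exact figures rest on those rates and on independence. The mixing of two kinds of use in one row does not.

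The window is a distinct inconsistency and needs no assumption about the eCRF. Read as looking back from consent, the SAP period shares max(0, 28 − s) days with the protocol's, none once s reaches 28. Its practical effect is on how medications are classified and listed.

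**What to change.** In SAP 6.6:

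1. Define prior medication as taken before the first dose on C1D1, collected from 4 weeks earlier, and concomitant medication as taken from the first dose to the short-term follow-up contact, in line with protocol 6.2.2.
2. Tabulate MT-3724 premedication separately. If it is captured on its own form, one sentence saying so, and that it stays out of the concomitant table, is enough for this step.
3. Tabulate medications given for a TEAE by ATC class and cohort, using the recorded reason for prescription. Presenting by cohort also meets protocol 7.8.1, which the SAP sentence does not address.

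The cost is SAP wording and one extra table. Reason for use is already collected, so no new data are needed, and no clinical rule changes.
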